Oral Medicine, Periodontology Oral Diagnosis and Oral Radiology Department Kafr Elsheikh University Faculty of Oral and Dental Medicine

Efficacy of Fascia Lata Allograft and Platelet Rich Fibrin versus Connective Tissue Graft on the Periodontal Phenotype Around Dental Implant in Upper Anterior Region: A Randomized Controlled Clinical Trial

Protocol of Thesis Submitted in Partial Fulfillment of the Requirements for Doctor

Degree in Periodontology

1/1/2024

Introduction

Nowadays, dental implants offer a reliable therapeutic option for tooth replacement therapy. However, along with the widespread application of dental implants, the risk of periimplant disease has emerged. The new classification of peri-implant diseases and condition are classified the peri-implant diseases into peri-implant health, peri-implant mucositis, periimplanitis, soft and hard tissue deficiencies. ⁽¹⁾

Peri-implant health is characterized by the absence of erythema, bleeding on probing, swelling, and suppuration. The main clinical characteristic of peri-implant mucositis is bleeding on gentle probing. Erythema, swelling, and/or suppuration may also be present. Peri-implantitis is a plaque-associated pathological condition occurring in tissues around dental implants, characterized by inflammation in the peri-implant mucosa and subsequent progressive loss of supporting bone. The evidence is equivocal regarding the effect of keratinized mucosa on the long- term health of the peri-implant tissue. It appears, however, that keratinized mucosa may have advantages regarding patient comfort and ease of plaque removal. Hard- and soft-tissue deficiencies at dental implants are common clinical findings. They can lead to complications and compromise implant survival and, hence, may require therapeutic interventions.⁽²⁾

The term "periodontal phenotype" comprises two terms, gingival phenotype (gingival thickness and keratinized tissue width) and bone morphotype (buccal bone plate thickness). Periodontal phenotype can be evaluated through clinical or radiographic assessments and may be divided into invasive/non-invasive (for gingival thickness), static/functional (for keratinized tissue width), and bi/tridimensional (for buccal bone plate thickness) methods. ⁽³⁾

The connective and support tissue around the implant keeps and protects the implant as it is in natural teeth. ⁽⁴⁾ Unlike natural teeth, the parallel course of connective tissue fibrils around the implant abutment creates a weaker sulcular barrier area. So, Sufficient amount of keratinized gingiva around the implant protects the connective and supporting tissue by reducing the accumulation of plaque and creating an immobile gingival sulcus. There is a consensus about the positive effects of keratinized tissue width on the survival rate of dental implants. The proper width and thickness of the gingival connective tissue has been proven to be one of the success criteria in dental reconstructive surgery. ⁽⁵⁾

Good quality soft tissue determines the possibility not only to obtain full primary wound closure during the bone defect reconstruction, but also assures effective implant treatment. ⁽⁶⁾ Moreover, it is very important to assure the proper emergence profile of the implant supported restoration, which gives the opportunity to achieve the highest aesthetic appearance. ⁽⁷⁾

Thick, soft tissue helps to prevent the development of an inflammatory reaction and clinical attachment level loss (CAL), as well as alveolar bone loss. Besides, it prevents gingival recessions arising, which have an influence on the final aesthetics and on the likelihood of developing inflammatory complications. ⁽⁸⁾ They found that the initial gingival tissue thickness at the crest may significantly affect the marginal bone loss (MBL) around implants and when the soft tissue was less than 2.0 mm thick, more crestal bone loss appears. ⁽⁹⁾

Augmentation is a method to gain keratinized gingiva and various graft alternatives can be used in an augmentation. Augmentations with autogenous grafts are preferred due to the low costs and less complications however, connective tissue grafting showing some operative difficulties like connective tissue harvesting, the possibility of bleeding, technique sensitivity in addition to postoperative complications like bleeding from the donor site, pain, patient discomfort, and delayed wound healing. ⁽¹⁰⁾ Alternative allograft materials have been developed to eliminate the disadvantages of autogenous grafts. ⁽¹¹⁾

Connective tissue graft (CTG) is the best choice for peri-implant soft tissue augmentation. ⁽¹²⁾ From the biological point of view, SCTG has the potential to induce the differentiation of mesenchymal cells into fibroblasts, which promotes epithelial proliferation and, consequently, helps modulate the soft tissue phenotype. ⁽¹³⁾ Nevertheless, postoperative donor-site morbidity, bleeding, infection, necrosis, limited availability of graft tissue, and the possible patient's discomfort at the second surgical site are the main drawbacks of such treatment modality. ⁽¹⁴⁾

A novel allogenic-derived acellular matrix produced from human fascia lata allograft (FLA) has been authorized as a viable alternative to soft tissue grafts and SCTGs in periodontal plastic surgery, ridge augmentation, socket grafting, as well as gingival recession and intraoral soft tissue abnormalities. ⁽¹⁵⁾ Fascia lata offers the advantage of eliminating the morbidity associated with human donor tissue, as well as being more widely available, affordable, and scalable. The antigenic cellular components are eliminated without compromising the structural integrity of the tissue, while leaving the extracellular collagenous matrix intact. ⁽¹⁶⁾

Platelet rich fibrin (PRF) has been introduced as an alternative to the SCTG to augment the gingival phenotype. It consists of a fibrin network containing platelets and a variety of growth factors, including transforming growth factor-beta1 (TGF- β 1), platelet-derived growth factor (PDGF), vascular endothelial growth factor (VEGF). ⁽¹²⁾ These molecules are slowly released and act directly to promote the proliferation and differentiation of fibroblasts. Even though the efficacy of applying PRF membrane in improving peri-implant soft tissue phenotype has been reported, more research work is still required to investigate its clinical performance. ⁽¹⁷⁾ PRF efficacy in optimizing and preserving the existing osseous structure and gingival architecture across peri-implant need to be corroborated. Shetty et al. in their study demonstrated that the placement of PRF membrane over denuded root surface in conjunction with coronally advanced flap results in the improvement in the thickness of gingiva. ⁽¹⁸⁾ In the long-term, the correct width and thickness of the attached keratinized tissue is the key point to ensure the stable position of the gumline around the implant's neck. ⁽¹⁹⁾ Therefore, the aim of this study was to improve periodontal phenotype surrounding the dental implants placed in patients to prevent any possible future complications which may occur.

Aim of the study

To compare between the efficacy of fascia lata allograft and platelet rich fibrin versus subepithelial connective tissue graft on periodontal phenotype (thickness and width of keratinized tissue, labial bone thickness) around dental implant in upper anterior region.

Materials and Methods

Study Design:

The present study will be conducted as a randomized controlled clinical study,

Study setting:

The study will be conducted in the clinic of Oral Medicine, Periodontology, Oral Diagnosis and Oral Radiology Department, Faculty of Dentistry, Kafer El sheikh University.

Ethical approval:

Before the treatment, the purpose of the study and the surgical procedures will be

explained to the patients who will be selected to participate in the study and an informed consent will be obtained from all patients before the beginning of any dental treatment by presenting the available three treatment options which were used in this study, representing the possible complications which may occur due to the presence of thin gingival biotype at the site of future implant placement, and the possible post-surgical complications which may occur after implants placement such as possible pain, post-operative bruising and extra-oral swelling.

Participation in the study is voluntary and stated the possibility to withdraw at any time. An official permission to conduct the study will be obtained from the Research Ethics Committee (REC), Faculty of Dentistry, Kafer El sheikh University. The research will be conducted in compliance with the 2004 revision of the Declaration of Helsinki. Confidentiality of the information where it will not be accessed by any other part without taking permission of the participants.

Sample size calculation:

Totally 24 patients. Allocated equally into three groups, 8 patients treated with subepithelial connective tissue graft (SCTG), another 8 patients treated with platelet-rich fibrin (PRF)graft, and another 8 patients treated with Fascia Lata Allograft.

Sample size was calculated using the G*power, version 3.1.9.2, Universität Kiel, Germany based on comparing the pink esthetic score six months after implant placement (T1) among patients treated with SCTG and PRF (Elkashty, A.A., et al.,2022)

Mean \pm SD of T1 among patients treated with SCTG = 5.1 ± 0.99

Mean \pm SD of T1 among patients treated with PRF = 3.5 ± 1.1

 α error probability = 0.05

Power $(1-\beta \text{ error probability}) = 0.80$

So, the sample size for each group will be 8 patients.

Site selection:

Twenty-four patients diagnosed with missing upper anterior due to factors other than periodontally involvement based on clinical and radiographically examination and fulfill the following eligibility criteria:

Inclusion criteria:

- 1. Patients age ranged from 20 to 50 of both genders.
- 2. Patients are systemically medically free according to the American Society of Anesthesiologists (ASA) considered as ASA I. ⁽²⁰⁾
- 3. Patients with thin gingival biotype (gingival thickness was $\leq 1 \text{ mm}$)
- 4. The height of keratinized gingiva (HKG) for the site selected should be ≥ 2 mm.
- 5. Ability to maintain good oral hygiene as evidenced in recall visits.
- 6. Sufficient mesiodistal and interocclusal space and have an intact facial bone wall which does not require bone augmentation procedures.
- 7. Adequate bone quality.
- 8. Ability to maintain good oral hygiene as evidenced in recall visits.

Exclusion criteria:

- 1. Smoker patient and pregnant or lactating woman.
- 2. Patient with poor oral hygiene or active periodontal disease.
- 3. Traumatic occlusion or para-functional habits such as clenching or bruxism.
- 4. Patient with limited mouth opening.

5. Participation in other clinical trials

Materials:

- 1) Implant system* Dual implant
- 2) Fasia lata allograft from Maxxeus company
- 3) PRF will be prepared according to Choukroun et al. ⁽²¹⁾
- 4) CTG will be taken according to Langer & Langer⁽²²⁾

Study design:

1) Patients group:

Patients were classified into three main groups:

- Group 1 (Study group)

It includes eight patients seeking for implant placement in the upper anterior areas and implants will be placed with the application of fascia lata allograft membrane.

- Group 2 (Study group)

It includes eight patients seeking for implant placement in the upper anterior area and implants will be placed with the application of PRF.

- Group 3 (Control group)

It includes eight patients seeking for single implant placement at the upper anterior area and those patients will be received their implants with subepithelial connective tissue graft.

2) Pretreatment preparation before surgery:

All the patients participate in this study regarding the patient's groups will undergo:

- 1. History taking, examination and preoperative laboratory investigation (bleeding tendency tests, HIV, HBV and HCV) to confirm suitability to the eligibility criteria.
- 2. A cone beam computed tomography (CBCT) will be taken to confirm the diagnosis and evaluate bone level and bone density.
- Occlusal adjustment will be done in cases with clinical and radiographic evidenced trauma of occlusion.
- 3) Phase I therapy:

All the patients will undergo comprehensive phase I therapy and re-evaluation will be done after 4 weeks to evaluate the patient response to phase I therapy.

4) Surgical phase:

Implant placement:

1- Group 1: (Dental implant + Fasia lata)

Preparation of the alveolus for delayed dental implant placement will be done according to manufacturer instructions and fasia lata will be fixed around dental implant.

2- Group 2: (Dental implant + PRF)

Preparation of the alveolus for delayed dental implant placement will be done according to manufacturer instructions and PRF will be fixed around dental implant.

3- Group 3: (Dental implant + CTG)

Preparation of the alveolus for delayed dental implant placement will be done according to manufacturer instructions and CTG will be fixed around dental implant.

5) Postoperative care:

All patients will receive post-operative instructions including, rinsing with 0.2% chlorhexidine (twice daily for 2weeks), For postsurgical pain control, 600 mg ibuprofen every 4 to 6 hours was

prescribed, and 500 mg amoxicillin was prescribed 3 times daily for 7 days to prevent infection. The patient was instructed to avoid brushing and trauma to the surgical site.

6) Prosthetic phase:

The final implant impression restoration will be made after 6 months from the surgery and fabrication of the abutment.

Clinical assessment:

The patients will be recalled at two weeks, month, 3 months, and 6 months post-surgery to record the clinical parameter which will be recorded by the same doctor.

A. The following clinical parameters will be recorded:

1- Pink aesthetic score (PES) (23) (Table 1)

Parameter	0	1	2
Mesial papilla	Missing	Incomplete	Complete
Distal papilla	Missing	Incomplete	Complete
Tissue contour	Unnatural	Virtually natural	Natural
Gingival level	>2mm	1-2 mm	1 mm
Alveolar process	Clearly resorbed	Slight resorbed	No difference
Coloring	Clear difference	Slight difference	No difference
Texture	Clear difference	Slight difference	No difference

2- Wound healing index (WHI): will be recorded at 7,14 days 1 and 3months according to

Huang et al. (24)

3- Gingival thickness (GT) will be measured at the mid-buccal 2 mm apical to the free gingival margin (at baseline, 3 months, and 6 months post-surgery) by penetrating a probe into the tissue. ⁽²⁴⁾

4- Peri-Implant Periodontal Probing depth (PPD):

This index depends mainly on the usage of 0.5 mm Michigan O probe with graduations. Measurements were evaluated at six sites per each implant i.e., the distofacial surface, mid facial surface, mesiofacial surface, mesio-lingual surface, mid lingual surface, and disto-lingual surfaces of the implant. PPD was measured by taking the reading from the free gingival margin to the base of the pocket. The mean score of the implant was obtained by adding the six scores and dividing it by six. ⁽²⁹⁾ Measurements were recorded to the nearest 0.5 mm six months after implant placement (prosthetic phase) (T1) and three months after the prosthesis placement.

Radiographic Evaluation:

Marginal (crestal) bone loss (MBL):

Radiographic examination of the patients will be done firstly pre-operative then just after the surgical procedures as a base point and at six months follow-up period post-operative by using CBCT (Morita) device. On Demand3D program was used for image reconstruction and analysis. For the calculation of marginal (crestal) bone loss (MBL), the implant was used as a reference by adjusting the cross-sectional long axis in the center of the implant and bisecting it. A line was drawn parallel to the implant, starting at the crest of the bony cortical plate of bone and ending at the apical level of the implant; height was recorded in millimeters immediately, 6 months postoperative. The same process was repeated from the palatal direction.

Statistical analysis:

The data will be collected and tabulated where statistical analysis will be done using statistical package for social science software (SPSS version 20) and comparison between the studied groups will be performed.

References

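### The aim compares the grafts on three phenotype components, but only gingival thickness has a planned follow-up reading; keratinized tissue width and labial bone thickness have none

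*Combined protocol and SAP*

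**What the plan says.** The Introduction defines periodontal phenotype as "gingival phenotype (gingival thickness and keratinized tissue width) and bone morphotype (buccal bone plate thickness". The Aim of the study takes up the same three components: the grafts are to be compared "on periodontal phenotype (thickness and width of keratinized tissue, labial bone thickness) around dental implant in upper anterior region".

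The rationale gives keratinized tissue weight of its own. The Introduction states "Augmentation is a method to gain keratinized gingiva", and just before the aim it says that "the correct width and thickness of the attached keratinized tissue is the key point to ensure the stable position of the gumline" around the implant.

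Clinical assessment lists four numbered parameters: pink aesthetic score (PES), wound healing index (WHI), gingival thickness (GT) and probing depth (PPD). Radiographic Evaluation adds marginal bone loss (MBL). GT is read mid-buccally at baseline, 3 and 6 months.

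KTW appears as a patient-level quantity only in Inclusion criteria, item 4: "The height of keratinized gingiva (HKG) for the site selected should be" at least 2 mm. The pre-operative CBCT is taken "to confirm the diagnosis and evaluate bone level and bone density". Further CBCTs follow immediately after surgery and at 6 months. Statistical analysis names no endpoint.

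**The concern.** A trial answers its aim only through what it records. Here two of the three quantities named in the aim do not appear among the assessments. At the end of the study the investigators could report whether the grafts differ in thickness, but not whether any graft changed the width of keratinized tissue or the thickness of the labial plate.

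The two gaps differ in urgency. A clinical width not measured at a visit is gone, and the plan includes no photographs, casts or intraoral scans from which it could be reconstructed. Bone thickness is a property of images that the plan already obtains, so what is missing there is mainly the definition of the reading.

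**Working it through.** **Step 1. Components in the aim against planned readings.**

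| Component | Where it appears for the patient | Planned follow-up reading |
|---|---|---|
| Gingival thickness | Inclusion criterion (at most 1 mm); Clinical assessment, item 3 | Yes: 3 and 6 months, with baseline |
| Keratinized tissue width | Inclusion criterion only (at least 2 mm); no method given | None |
| Labial bone thickness | Intact facial wall required at entry; no value in mm | None |

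Components with a follow-up reading: 1 of 3.

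**Step 2. Does another listed outcome stand in for the missing two?**

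- The PES items rate papillae, contour, gingival level, alveolar process, colour and texture. None is KTW. The alveolar process item is a 0 to 2 rating of resorption, not a thickness.
- WHI and PPD measure neither width nor bone.
- MBL is taken along a line parallel to the implant, from the bone crest to the apical level, and recorded as a height. Thickness would be measured across that line.
- Applying the KTW entry criterion requires someone to look at the width before treatment, but the text does not say that the value in mm is retained.

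**Step 3. Nominal counts.** Inputs: 24 patients in three groups of 8 (Sample size calculation). Assumptions: one implant per patient and no withdrawals.

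- KTW readings not recorded at 3 and 6 months: 24 × 2 = 48.
- Planned CBCTs: 24 × 3 = 72. With the implant in place (immediate and 6 months): 24 × 2 = 48, that is, 24 pairs.

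Both assumptions can fail. Ethical approval says "Participation in the study is voluntary and stated the possibility to withdraw at any time", with no rate given. Patients group specifies one implant only for Group 3: "It includes eight patients seeking for single implant placement at the upper anterior area"; Groups 1 and 2 could therefore contribute more sites. If 0, 1 or 2 patients per group are lost after the immediate scan and before 3 months (an assumed range), N = 24, 21 or 18 remain:

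| N | KTW follow-up readings, 2N | Post-implant scans, 24 + N | All scans, 48 + N | Scan pairs, N |
|---|---|---|---|---|
| 24 | 48 | 48 | 72 | 24 |
| 21 | 42 | 45 | 69 | 21 |
| 18 | 36 | 42 | 66 | 18 |

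**Step 4. Is the sample size affected?** The plan's figure is 8 per group, for PES at 6 months. Difference = 5.1 − 3.5 = 1.6. Pooled SD = √[(0.99² + 1.1²)/2] = 1.046. Standardized difference = 1.6/1.046 = 1.529. A two-sample t-test at α = 0.05 (two-sided assumed; the plan does not say) with power 0.80 gives n = 7.80, rounded up to 8, with power 81.1%. The plan's figure reproduces. It rests on PES, which is not one of the three components, so neither the gap nor its repair changes it.

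**The case against.** The best defence is that thickness is the deficiency this trial selects for. Entry requires thin tissue and at least 2 mm of keratinized gingiva, the consent discussion concerns thin biotype, and thickness is measured three times. The passages on keratinized width are general background, and the Introduction itself calls the evidence on keratinized mucosa and long-term health equivocal. This tempers how central KTW is. It does not answer the aim, which names width and labial bone alongside thickness.

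A second objection concerns timing. PPD is also read three months after the prosthesis is placed, and KTW could be read at that contact. This stands in part: a later comparison between groups would be possible. But it is not planned. Since the final impression comes after 6 months, it would fall no earlier than 6 + 3 = 9 months after surgery. It would not replace the 3- and 6-month values.

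Third, text may have been lost: PPD cites reference 29, while the list ends at 26, and references 25 and 26 are not cited in the text. However, the clinical parameters run from 1 to 4 without a gap or redaction mark, so a dropped KTW item is possible but not indicated.

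A reader might also infer that the reference point for GT is undefined. It is not: the protocol names the free gingival margin. What it leaves open is how that margin is located at an edentulous baseline site and before the final restoration. A KTW reading would need the same answer.

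**Conclusion.** The mismatch holds. Two of the three components in the aim have no planned post-treatment value, and the plan followed exactly cannot compare the grafts on them. The KTW half makes this a point to settle before follow-up readings are missed: nominally 48 values at 3 and 6 months, under the assumptions of one implant per patient and no withdrawals.

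Two stronger readings are not supported. One is that all chance of comparing KTW is lost; only the unrecorded 3- and 6-month values are, and an unplanned later reading remains possible. The other is that bone thickness is safely recoverable. That assumes the scans are stored and the thin labial plate can be read beside an implant, and the documents state neither. On those assumptions the bone gap is the lesser of the two.

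**What to change.** **Keratinized tissue width.** Record mid-buccal KTW in mm at baseline, 3 and 6 months, when GT is measured, from the mucogingival junction to the coronal reference used for GT. State how the free gingival margin is located at the edentulous baseline site and before the final restoration. Compare groups at 6 months with baseline as covariate.

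**Labial bone thickness.** Measure it at one pre-named distance from the implant platform on the immediate post-operative and 6-month CBCTs, in the cross-section used for MBL. State that the scans are kept. Define the reading before any comparison of groups. Compare groups at 6 months with the immediate post-operative value as covariate.

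Report both as secondary outcomes with confidence intervals. If either is not added, narrow the aim to what is measured.

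**Cost.** Protocol wording, a few minutes of measurement per patient, and two more outcomes (five listed become seven). No added visit or scan, and no change to the sample size. Narrowing the aim costs only wording but gives up the omitted component.

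### Does the hygiene criterion judged at recall visits, or the word 'single' in one group description, let patients be selected after allocation or differently by arm?

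*Combined protocol and SAP*

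**What the plan says.** All locations are in the combined protocol and SAP.

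- **Inclusion criteria, items 5 and 8**, are identical: "Ability to maintain good oral hygiene as evidenced in recall visits".
- **Clinical assessment** is the only section that speaks of recalling patients: "The patients will be recalled at two weeks, month, 3 months, and 6 months post-surgery". The assessments listed there are PES, wound healing index, gingival thickness and peri-implant probing depth.
- **Pretreatment preparation before surgery, item 1**, has history, examination and laboratory tests done "to confirm suitability to the eligibility criteria".
- **Exclusion criteria, item 2**, reads "Patient with poor oral hygiene or active periodontal disease" and does not refer to recall visits.
- **Phase I therapy**, which precedes the surgical phase, states that "re-evaluation will be done after 4 weeks to evaluate the patient response to phase I therapy".
- **Study design, patient groups**: Group 3 (control) is described as seeking a single implant. The word is absent for Groups 1 and 2, and Group 1 has 'areas' in the plural.
- **Sample size calculation** counts patients: 24 in total, 8 per group.

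**The concern.** An entry criterion should be decidable before allocation. If hygiene is judged at visits from two weeks to six months after surgery, it is an outcome of the treatment period. The protocol offers some reasons why it might vary with the graft:

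- Under Postoperative care, "The patient was instructed to avoid brushing and trauma to the surgical site".
- The Introduction says of the connective tissue graft that the patient's possible "discomfort at the second surgical site are the main drawbacks of such treatment modality", and only the control arm has such a site.
- The Introduction also says "keratinized mucosa may have advantages regarding patient comfort and ease of plaque removal", and the grafts are meant to improve that tissue.

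Dropping patients on such a variable would weaken the protection of randomisation, and one patient is 1/8 = 12.5% of an arm. The protocol states neither the time of allocation nor an analysis population, so nothing expressly forbids it.

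The group descriptions raise a second question. If a patient needing several implants could enter only Groups 1 and 2, case mix would differ by arm. Counting implants as independent observations would then understate standard errors.

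**Working it through.** **1. The plan's own figure.** Inputs from Sample size calculation: mean PES 5.1 (SD 0.99) for the connective tissue graft, 3.5 (SD 1.1) for PRF, alpha 0.05, power 0.80. Sidedness is not stated; two-sided is assumed.

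- Pooled SD = sqrt((0.99² + 1.1²)/2) = 1.046
- Standardised difference = (5.1 − 3.5)/1.046 = 1.529
- Two-sided t-test power: 0.811 with 8 per group, 0.747 with 7 per group

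The 8 per group reproduces, with the patient as the unit.

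**2. When is hygiene judged?** Four features of the text point to a pre-surgical judgement.

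- The 24 patients must meet the criteria in order to be selected, and suitability is checked before surgery.
- The post-surgical recalls exist to record named clinical parameters. None is a plaque or hygiene index, so those visits supply no means of applying the criterion.
- Poor hygiene is excluded separately, with no link to recall.
- All patients return for the 4-week re-evaluation after phase I therapy, before surgery. It is not called a recall and does not name hygiene, but it is a workable occasion for the judgement.

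**3. Would removal differ by arm?** The no-brushing advice belongs to instructions given to all patients, so it cannot separate the arms. The donor-site text concerns morbidity and discomfort, not plaque control. The keratinized-mucosa sentence says only that there may be an advantage, directly after calling the evidence on long-term health equivocal.

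**4. How large could it be?** Suppose one arm alone loses its worst patient of 8 on hygiene, and hygiene correlates with PES at ρ = 0.3 to 0.5. Both suppositions are assumptions; neither is in the documents. The expected minimum of 8 standard normal values is −1.424.

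- Shift in arm mean = ρ × 1.424 × 1.046/7
- Standard error of a difference between two arms of 8 = 1.046 × sqrt(2/8) = 0.523

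| Case | Shift (PES points) | Share of 1.6 | Share of standard error |
|---|---|---|---|
| ρ = 0.3 | 0.064 | 4.0% | 12% |
| ρ = 0.5 | 0.106 | 6.7% | 20% |
| Removed patient 2 points (1.9 SD) below the arm mean | 2/7 = 0.286 | 17.9% | 55% |

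Power with 7 against 8 would be 0.780.

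**5. Implant number.** The plural 'implants' appears in all three group descriptions, Group 3 included, so it can refer to the eight patients together. The surgical text is the same in every arm and fixes the graft around one implant. The aim refers to a dental implant in the singular, and inclusion item 4 to one selected site. One eligibility list covers all 24 patients.

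Type I error would rise only if every study-arm patient had two implants and these were analysed as independent. Against a single-implant control of 8, the variance ratio is (1/8 + (1 + ICC)/16)/(1/8 + 1/16) = 1.10 to 1.23 for an assumed ICC of 0.3 to 0.7. Then 2 × P(Z > 1.96/sqrt(ratio)) = 0.062 to 0.078. None of these conditions is in the documents.

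**The case for a change.** The strongest opposing case is that the benign reading is inferred. The 4-week re-evaluation is never called a recall, does not mention hygiene, and is listed after the eligibility check. The Statistical analysis section is brief, with no analysis population and no rule on exclusions after allocation. At 8 per arm there is little slack: losing one patient takes power from 0.811 to 0.780, below the planned 0.80. Probing depth is averaged per implant, and no sentence fixes the unit of analysis.

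Much of this is true as description. The duplicate is real, the recall wording is loose, and 'single' is used for one arm only. What does not stand is the step to harm. It needs hygiene to be judged after surgery without any listed measure, a treated patient to be removed without any provision for it, and removals to be uneven across arms. The power loss follows from losing any patient for any reason and is not specific to this criterion. Averaging six probing sites gives one score for an implant; it does not make several implants in one patient independent units. The missing analysis population is a separate gap and does not turn this criterion into a source of bias.

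**Conclusion.** The concern does not hold as a statistical defect. Items 5 and 8 are a duplicated line with loose wording about the visit, and the Group 3 wording is most likely a drafting slip. With eligibility confirmed before surgery and one patient as one unit, as the sample size has it, the randomised comparison is unaffected on this point. An analyst would proceed that way without further instruction.

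Even granting a hygiene-based removal confined to one arm, the expected shift is 0.06 to 0.11 PES points, or 12 to 20% of one standard error. The constructed extreme is 0.29 points, about 55% of one standard error. These sizes rest on the assumed correlation and the assumed removal. The type I error of about 6 to 8% rests on assumed two-implant patients and an implant-level analysis that the plan does not describe, so it carries no weight here. Removing the repeated line and aligning the group descriptions would be ordinary editing; neither the design nor the analysis depends on it.

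### Does the plan need a pink aesthetic score (PES) taken with the final restoration in place?

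*Combined protocol and SAP*

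**What the plan says.** Clinical assessment sets the general visits: "The patients will be recalled at two weeks, month, 3 months, and 6 months post-surgery to record the clinical parameter". The first item under it, "1- Pink aesthetic score (PES) (23) (Table 1", is followed by a scoring table and no times. The other three clinical parameters state their own times: wound healing at days 7 and 14 and at 1 and 3 months; gingival thickness at baseline, 3 and 6 months; and probing depth "six months after implant placement (prosthetic phase) (T1) and three months after the prosthesis placement".

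Under Prosthetic phase, "The final implant impression restoration will be made after 6 months from the surgery and fabrication of the abutment". Under Radiographic Evaluation, the last CBCT is "at six months follow-up period post-operative by using CBCT (Morita) device".

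Sample size calculation rests on "comparing the pink esthetic score six months after implant placement (T1"), with the connective tissue graft and platelet-rich fibrin arms as the pair compared, and ends: "So, the sample size for each group will be 8 patients". Aim of the study names tissue thickness and width and labial bone thickness, and does not name PES.

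**The concern.** PES is the outcome on which the trial was sized, yet its entry does not say when it is scored. If the recall list governs, every PES score is taken no later than the start of the prosthetic phase. The trial would then have no aesthetic score on a restored implant, although the Introduction connects appearance with the restoration that the implant carries. Probing depth does have a reading after fitting, so the plan appears to use a later visit for one parameter and pass it over for the aesthetic one. If that visit takes place and PES is not scored, the score cannot be recovered afterwards.

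**Working it through.** **Timing.** Inputs are the recall list, the Prosthetic phase paragraph and the probing-depth entry.

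| Measure | Times | After fitting |
|---|---|---|
| PES (by default from the recall list) | 2 weeks, 1, 3, 6 months | 0 of 4 |
| Probing depth | 6 months (T1); 3 months after fitting | 1 of 2 |

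The impression is made after 6 months, so the later probing-depth reading falls at 6 + 3 = 9 months or later. The recall list has no such visit.

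The PES row is an inference. None of the three parameters with stated times follows the recall list exactly: wound healing adds day 7, gingival thickness uses baseline, 3 and 6 months, and probing depth adds the later reading. The list is therefore a weak guide to when PES is scored. What the text supports is that PES times are not stated. A score after fitting is not scheduled, but it is not ruled out either.

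**The plan's own figure.** Inputs from Sample size calculation: means 5.1 and 3.5, SDs 0.99 and 1.1, alpha 0.05, power 0.80. Sidedness is not stated; two-sided is assumed.

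- Difference = 5.1 − 3.5 = 1.6.
- Pooled SD = √((0.99² + 1.1²)/2) = √1.095 = 1.046.
- d = 1.6/1.046 = 1.53.
- Power of the two-sample t-test (noncentral t): 0.747 at n = 7 per group and 0.811 at n = 8.

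The smallest n that reaches 0.80 is 8, as stated. The figure belongs to the six-month score, and six months is one of the recall visits. A later score reported without a test leaves n, alpha and power as they are.

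**What a later score would offer.** PES has 7 items scored 0 to 2, so it runs from 0 to 14. The 95% half-width for a two-group difference is t(0.975, 2n − 2) × SD × √(2/n). The SD after fitting is not given, so the six-month 1.046 is carried forward as an assumption, with 0.8 to 1.5 as a range. Losses of one or two patients per group are also assumed.

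| n per group | Scores in total | SD 0.8 | SD 1.046 | SD 1.5 |
|---|---|---|---|---|
| 8 | 24 | ±0.86 | ±1.12 | ±1.61 |
| 7 | 21 | ±0.93 | ±1.22 | ±1.75 |
| 6 | 18 | ±1.03 | ±1.35 | ±1.93 |

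At SD 1.046 every half-width is below the planning difference of 1.6. Width reaches 1.6 only at an SD of about 1.49 with n = 8 (1.6/(2.145 × 0.5)) or 1.24 with n = 6 (1.6/(2.228 × 0.577)). So imprecision would not be what makes a later score descriptive. The reasons would be that six months is the time the trial was sized for, and that testing a second time raises a multiplicity question. The half-widths do not measure any harm from the present plan.

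**The case for a change.** The best case for a change is that it would be cheap. If the post-fitting visit goes ahead, up to 24 visual scores could be added there with no effect on the sample size or on any existing reading. The plan would then show how the tissue looks around the finished restoration, which is of natural interest in an upper anterior trial. The plan's own text also needs reconciling, because the recall list omits both the later probing-depth visit and the day-7 wound-healing reading.

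The scheduling mismatch stands as a matter of fact. The low cost is conditional: the recall list and the gingival-thickness and CBCT schedules all end at six months, so the later visit depends on one sentence. If it is not held, the extra score would need up to 24 new visits. Losses are possible, since "Participation in the study is voluntary and stated the possibility to withdraw at any time", and the enrolled number equals the calculated number with no margin.

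The argument from aesthetic interest is weaker. The PES table scores papillae, contour, gingival level, alveolar process, colour and texture; no item scores the crown. These items might read differently once a crown is in place, but the documents give no evidence either way. The Introduction sentence concerns soft tissue and emergence profile and says nothing about when to score.

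**Conclusion.** No change to the plan follows. A six-month PES is the outcome and time on which the sample size was based, and the recall list provides that visit. The stated 8 per group stands, with power 0.811 for the one comparison used, assuming a two-sided t-test. No figure, test or conclusion depends on whether PES is scored again after fitting. The stated aim is phenotype, so a later aesthetic score would be a supplementary description and would correct nothing.

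What remains is missing detail. The recall list and the T1 label supply a sensible reading for PES, with six months as the time that counts. Whether probing depth is read after fitting, and on which visit day 7 falls, are scheduling points for the study team. Should the later visit be held, scoring PES there is a fair option but not a requirement. This conclusion assumes that PES is in fact scored at the six-month recall, which the sizing statement and the recall list together imply but the PES entry does not say.
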